### **Secondary outcome 1**

The number (and percentage) of participants with: 1,2,3 or >3 attempts to be contacted prior to their hrHPV test.

Data obtained from participating GP clinics.

*Timepoint:*

By the end of screening period.

---

### **Secondary outcome 2**

The mean, median and range for time from the first study appointment to an hrHPV test being conducted, for each participant.

Data obtained from participating GP clinics.

*Timepoint:*

By the end of screening period.

---

### **Secondary outcome 3**

The mean, median and range for time from first the contact attempt to an hrHPV test being conducted, for each participant.

Data obtained from participating GP clinics.

*Timepoint:*

By the end of screening period.

---

### **Secondary outcome 4**

The number (and percentage) of participants who were successfully contacted to take part in the study by:

- Letter
- Text
- Opportunistic invitation at their GP clinic
- A face to face appointment with a staff member at their GP clinic
- A phonecall with a staff member from their GP clinic
- Other form of contact.

Data obtained from participating GP clinics.

*Timepoint:*

By the end of screening period.

---

### **Secondary outcome 5**

The mean, median and range for the time from an hrHPV test being undertaken to being received by the laboratory for analysis, for each participant.

Data to be presented separately by whether participants had an hrHPV test at home or at their GP clinic.

Data obtained from participating GP clinics and laboratories.

*Timepoint:*

By six months after the end of the screening period.

---

### **Secondary outcome 6**

The mean, median and range of charges (NZD) for each type of hrHPV test listed under Primary Outcome 1 above.

This will be reported by whether the tests were subsidised or not.

Data obtained from participating GP clinics.

*Timepoint:*

By the end of screening period

---

### **Secondary outcome 7**

The mean, median and range for the time from an hrHPV test to the results report being issued.

Data obtained from participating GP clinics and laboratories.

*Timepoint:*

By six months after the end of the screening period.

---

**Secondary outcome 8**

In participants who underwent hrHPV testing and had an unsatisfactory result, the reason for that result:

- Incorrect labelling
- Sample unsatisfactory
- Other.

Data obtained from participating GP clinics and laboratories.

*Timepoint:*

By six months after the end of the screening period.

---

**Secondary outcome 9**

In participants who underwent hrHPV testing and had an unsatisfactory result, the number (and percentage) that:

- Did have a repeat hrHPV test
- Did not have a repeat hrHPV test.

Data obtained from participating GP clinics and laboratories.

*Timepoint:*

By six months after the end of the screening period.

---

**Secondary outcome 10**

In participants who underwent hrHPV testing and had a repeat test, the mean, median and range for the time from the first hrHPV test to the repeat hrHPV test.

Data obtained from participating GP clinics and laboratories.

*Timepoint:*

By six months after the end of the screening period.

---

**Secondary outcome 11**

The mean, median and range for the time from an hrHPV test result report being issued and the participant being informed of the result.

Data to be presented separately for participants negative for hrHPV, participants positive for HPV16 and/or 18, and participants positive for hrHPV other than 16 or 18.

Data obtained from participating GP clinics and laboratories.

*Timepoint:*

By six months after the end of the screening period.

---

### **Secondary outcome 12**

The number (and percentage) of participants informed of their hrHPV result by:

- Face to face appointment with a staff member at their GP clinic
- Phonecall with a staff member from their GP clinic
- Text
- Other form of contact.

Data to be presented separately for participants negative for hrHPV, participants positive for HPV16 and/or 18, and participants positive for hrHPV other than 16 or 18.

Data obtained from participating GP clinics.

*Timepoint:*

By six months after the end of the screening period.

---

### **Secondary outcome 13**

The reason cytology was performed in participants that had cytology results issued from the sample taken during a cervical hrHPV test:

- Requested by GP due to previous high grade lesion (test of cure)
- Requested by GP due to previous abnormal cytology
- Requested by GP due to symptoms
- Requested by GP for other reason
- Performed by lab due to detection of hrHPV (not GP requested)
- Performed by lab due to identification of need to test for cure (not GP requested),
- Other reason.

Data obtained from participating GP clinics and laboratories.

*Timepoint:*

By six months after the end of the screening period.

---

### **Secondary outcome 14**

The reason cytology was performed in participants that had cytology test\* performed after an hrHPV test and before colposcopy:

- Positive for hrHPV result
- Other reason.

\*Please note for this and subsequent outcomes the term “cytology test” refers to a cytology sample taken at a GP clinic after an hrHPV test and before colposcopy.

Data to be presented separately for participants negative for hrHPV, participants positive for

HPV16 and/or 18, and participants positive for hrHPV other than 16 or 18.

Data obtained from participating GP clinics.

*Timepoint:*

By six months after the end of the screening period.

---

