### **Figure 3 details**

*\*Note if a vaginal self-test is taken and the result is positive a cervical cytology specimen is indicated to stratify risk, however in some circumstances it will not change so is not required (i.e., HPV16/18 positive). If a cervical test has been taken this will be performed on the same specimen by the laboratory. It is advised that this test is performed within 2 weeks.*

*\*\*With the new five yearly screening interval, those coming in for their next screening test (after previous cytology screening) any time in the last five years before age 69, i.e., 65 – 69 years of age (inclusive), can exit the programme if their HPV test result is negative. This includes those with normal screening histories, with no screening history, and those with previous abnormalities who have already been returned to regular interval (three yearly) screening. See protocol for details of exceptions.*

[figure not shown]
*Those who would normally exit the NCSP under the current NCSP exit requirements i.e., have had two normal screening cytology samples between ages 62 and 69 years of age, can exit at 69 years of age without HPV testing (providing not immune deficient or requiring further follow-up because of abnormal results).*

*\*\*\*Urgency of referrals to Colposcopy are as follows;*

- *Very Urgent – Suspicion of Malignancy (10 working days)*
- *Urgent – High-grade cytology and/or HPV 16 or 18 positive (20 working days)*
- *Semi-Urgent – Other high-risk HPV and low-grade/ASCUS cytology (3 months)*
- *Colposcopy can be referred as a clinical override e.g., HPV other and patient declining cytology triage.*

Positive clinician-taken LBC cervical HPV samples had cytology performed by the laboratory. The result was sent to the requesting clinician and study staff, as well as directly to the NCSP by the laboratory. Positive HPV vaginal self-test samples cannot have cytology performed on them, so a separate clinician-taken cytology test at the participant's general practice was recommended.

Indications for colposcopy are outlined in Figure 4. Colposcopy was performed as per standard practice guidelines.

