### **Secondary outcome 19**

In participants that had a cytology test prior to colposcopy, the number (and percentage) with a result of:

- Negative for dysplasia or malignancy
- ASC-US (atypical squamous cells of undetermined significance - excluding ASC-US possible high grade)
- LSIL (low grade squamous intraepithelial lesion)
- ASC-H (atypical cells of undetermined significance, possible high grade)
- HSIL (high grade squamous intraepithelial lesion)
- Cancer (invasive squamous carcinoma of the cervix)
- Adenocarcinoma
- Cancer other
- AGC/AIS (atypical glandular cells / adenocarcinoma-in-situ)
- Unsatisfactory sample.

Data to be presented separately for participants negative for hrHPV, participants positive for HPV16 and/or 18, and participants positive for hrHPV other than 16 or 18.

Data obtained from participating GP clinics and laboratories.

*Timepoint:*

By six months after the end of the screening period.

---

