#### **Secondary outcome 26**

In participants that had a cytology test during colposcopy, the number (and percentage) with a result of:

- Negative for dysplasia or malignancy
- ASC-US (atypical squamous cells of undetermined significance - excluding ASC-US possible high grade)
- LSIL (low grade squamous intraepithelial lesion)
- ASC-H (atypical cells of undetermined significance, possible high grade)
- HSIL (high grade squamous intraepithelial lesion)
- Cancer (invasive squamous carcinoma of the cervix)
- Adenocarcinoma
- Cancer other
- AGC/AIS (atypical glandular cells / adenocarcinoma-in-situ)

- Unsatisfactory sample.

Data to be presented separately for participants negative for hrHPV, participants positive for HPV16 and/or 18, and participants positive for hrHPV other than 16 or 18.

Data obtained from participating GP clinics, laboratories and/or colposcopy clinics.

*Timepoint:*

By six months after the end of the screening period.

---

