**Secondary outcome 34**

Incidence of CIN2+ in participants by cytology result.

Data to be presented separately for participants negative for hrHPV, participants positive for HPV16 and/or 18, and participants positive for hrHPV other than 16 or 18.

Data obtained from participating GP clinics, laboratories and colposcopy clinics.

*Timepoint:*

By six months after the end of the screening period.

---

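### Table A1's definition of 'cytology test' leaves cytology read from the clinician-taken HPV specimen out of the cytology result outcome (19) and the linked outcomes 21 and 22

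*Protocol*

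**What the plan says.** The footnote to Secondary outcome 14 in Table A1 begins "Please note for this and subsequent outcomes the term" and goes on to say that 'cytology test' "refers to a cytology sample taken at a GP clinic after an hrHPV test and before colposcopy".

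The notes to Figure 3 describe two routes to cytology after a positive HPV result.

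- Clinician-taken test: "If a cervical test has been taken this will be performed on the same specimen by the laboratory". The text below those notes confirms it: "Positive clinician-taken LBC cervical HPV samples had cytology performed by the laboratory".
- Vaginal self-test: the swab cannot be used for cytology, so "a separate clinician-taken cytology test at the participant's general practice was recommended".

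Four later entries in Table A1 matter here.

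- Outcome 19, the cytology results: "In participants that had a cytology test prior to colposcopy, the number (and percentage) with a result of", followed by the list of grades.
- Outcome 26: "In participants that had a cytology test during colposcopy, the number (and percentage) with a result of", followed by the same list.
- Outcome 34: "Incidence of CIN2+ in participants by cytology result".
- Outcome 36 costs a cytology test done as part of the cervical HPV test.

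Outcome 13, which comes before the footnote, covers cytology on the cervical HPV sample but asks only why it was done.

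**The concern.** A sample taken at the HPV test is not a sample taken after it. Reflex cytology on a positive clinician-taken specimen, and cytology requested with a cervical HPV test (test of cure, symptoms), therefore fall outside the defined term. Any outcome built on that term loses them.

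The main casualty is outcome 19, the only tabulation of cytology results before colposcopy. As written, it would describe mainly self-testers who came back for a second visit, a self-selected group. It would leave out the group in which triage needs no return visit. Outcomes 21 (how participants were told their cytology result) and 22 (cytology report to colposcopy referral) lose the same people. Cytology triage is a named pathway step in the Figure 2 objectives, and the Statistical analysis section plans to stratify outcomes by self-taken or clinician-taken test. For these outcomes the clinician-taken stratum would be almost empty.

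The protocol also uses the term in ways its own definition forbids (outcomes 26 and 36). Two analysts could each defend their choice and produce different tables.

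**Working it through.** **Step 1: which outcomes the definition reaches.** The wording of each outcome from 13 onward that concerns cytology, set against the footnote:

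| Outcome | Wording | Cytology on the HPV specimen |
|---|---|---|
| 13 | sample taken at the cervical HPV test | covered, reason only |
| 14–17 | later cytology: reason, invitations, absence, delay | excluded or not relevant; the restriction suits the question |
| 18, 20 | defined term; times from sample to report and to notification | excluded; the interval would also differ, because HPV processing comes first |
| 19 | defined term; results | excluded |
| 21, 22 | defined term; notification route, report to referral | excluded |
| 26 | term used for cytology during colposcopy | conflicts with the definition |
| 34 | 'cytology result', not the defined term | not restricted |
| 36 | term used for cytology within the HPV test | conflicts with the definition |

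Outcome 19 also asks for a stratum of HPV-negative participants. The cytology that the protocol recommends regardless of HPV result (symptoms, test of cure) is taken with the cervical HPV test, which is what the definition removes.

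**Step 2: reproduce the plan's figures.** Inputs from the Sample size section: 3,000 participants, 60–70% choosing the self-test, 12% of self-tests positive.

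- 3,000 × 0.60 × 0.12 = 216
- 3,000 × 0.70 × 0.12 = 252

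Both match the protocol. This is the group for whom separate later cytology is planned, so it is the group the definition keeps.

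**Step 3: size the omitted group.** Clinician-taken tests number 3,000 × 0.30 = 900 to 3,000 × 0.40 = 1,200. The protocol gives no positivity for them. The table takes 12% as the central assumption and 8–15% as the range. Share = omitted ÷ (omitted + self-test positives).

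| Assumed cervical positivity | 900 clinician-taken (252 self-test positives) | 1,200 clinician-taken (216 self-test positives) |
|---|---|---|
| 8% | 72; 72/324 = 22% | 96; 96/312 = 31% |
| 12% | 108; 108/360 = 30% | 144; 144/360 = 40% |
| 15% | 135; 135/387 = 35% | 180; 180/396 = 45% |

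These are shares of expected HPV-positive participants, not of cytologies done. Not every self-test positive will return for cytology, and the Figure 3 notes say that in some circumstances (HPV 16/18) it is not required. Cytology in HPV-negative participants comes on top and cannot be sized from the protocol.

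**The case against.** The strongest reply is that this is a loosely worded footnote and not a decision to drop a group. Outcomes 26 and 36 depart from it where the context requires, and in outcome 26 the specific wording plainly governs. Outcomes 14–17 are about the extra visit, which is the protocol's own sizing concern, and there the restriction is right. Figure 2 states the result outcome without the restriction, but it is an overview that sends the reader to the table for detail, so that difference is weak evidence of a contradiction. No data are lost, since the study laboratory's cytology results are collected. All of this stands. It limits the point to outcome 19 and its neighbours and suggests a drafting slip. It does not remove the gap, because outcome 19 followed as written still omits these results.

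A reader might infer more:

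- **That CIN2+ by cytology result also loses the clinician-taken group.** The footnote defines 'cytology test'; outcome 34 says 'cytology result' and is not caught.
- **That no comparison of triage by test type is possible.** Primary outcome 3 gives time from HPV report to referral separately for cervical and vaginal tests, and for referral with and without cytology. Outcome 23 reports referral urgency whatever the cytology source.
- **That outcome 26 is an empty set.** Its own words say which samples are meant.
- **That 30–40% of cytology results are lost.** That figure is a share of HPV positives under an assumed equal positivity. Equal positivity is uncertain, because participants with symptoms or due a test of cure were advised to have the cervical test.

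**Conclusion.** The point holds in a limited form. Read literally, Table A1 excludes cytology on the clinician-taken HPV specimen from outcome 19 and from the linked outcomes 21 and 22, and no outcome tabulates the distribution of those results. Comparison by test type is impaired for that distribution and the linked steps only.

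Under equal 12% positivity about 108 to 144 HPV-positive participants are affected, and 72 to 180 across 8–15%. This rests on the protocol's planned 3,000 participants and 60–70% self-test share, not on what was recruited. The defect lies in a stated definition that conflicts with the document's own usage, so it is more than detail left for an analysis plan. It concerns secondary, descriptive tables and should be corrected before they are fixed.

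**What to change.** Reword the footnote and name two sources: cytology on the HPV specimen (reflex or requested with the test), and separate GP cytology taken later.

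- Limit the present definition to outcomes 14–17.
- For outcomes 19, 21 and 22, include both sources, shown by source and HPV group.
- If outcomes 18 and 20 are extended to the HPV specimen, report the two sources separately and do not pool them, because the intervals differ.
- State that outcome 34 uses both sources.
- State that outcomes 26 and 36 lie outside the definition.

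The cost is one reworded footnote and a few extra table columns. No new data are needed, since the Outcome measures and data management section already lists HPV and cytology results from the study laboratory. The protocol reports analysis as in progress, so the clarification should be dated and should record whether the affected tables had been produced by then.

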### **Secondary outcome 15**

The number (and percentage) of participants with 0, 1, 2 or 3 invitations for a cytology appointment, in participants who are recommended to have cytology.

Data to be presented separately for participants negative for hrHPV, participants positive for HPV16 and/or 18, and participants positive for hrHPV other than 16 or 18.

Data obtained from participating GP clinics.

*Timepoint:*

By six months after the end of the screening period.

---

### **Secondary outcome 16**

The reason for no cytology report (prior to colposcopy) in participants positive for hrHPV and had a vaginal hrHPV test:

- Cytology not considered feasible by the GP
- Participant declined
- Participant unable to be contacted
- Other.

Data to be presented separately for participants positive for HPV16 and/or 18 and participants positive for hrHPV other than 16 or 18.

Data obtained from participating GP clinics.

*Timepoint:*

By six months after the end of the screening period.

---

### **Secondary outcome 17**

In participants that had a cytology test prior to colposcopy, the mean, median and range for the time between an hrHPV test result report being issued and a cytology sample being undertaken.

Data to be presented separately for participants negative for hrHPV, participants positive for HPV16 and/or 18, and participants positive for hrHPV other than 16 or 18.

Data obtained from participating GP clinics and laboratories.

*Timepoint:*

By six months after the end of the screening period.

---

### **Secondary outcome 18**

In participants that had a cytology test prior to colposcopy, the mean, median and range for the time from a cytology sample being undertaken to the results report being issued.

Data to be presented separately for participants negative for hrHPV, participants positive for HPV16 and/or 18, and participants positive for hrHPV other than 16 or 18.

Data obtained from participating GP clinics and laboratories.

*Timepoint:*

By six months after the end of the screening period.

---

### **Secondary outcome 19**

In participants that had a cytology test prior to colposcopy, the number (and percentage) with a result of:

- Negative for dysplasia or malignancy
- ASC-US (atypical squamous cells of undetermined significance - excluding ASC-US possible high grade)
- LSIL (low grade squamous intraepithelial lesion)
- ASC-H (atypical cells of undetermined significance, possible high grade)
- HSIL (high grade squamous intraepithelial lesion)
- Cancer (invasive squamous carcinoma of the cervix)
- Adenocarcinoma
- Cancer other
- AGC/AIS (atypical glandular cells / adenocarcinoma-in-situ)
- Unsatisfactory sample.

Data to be presented separately for participants negative for hrHPV, participants positive for HPV16 and/or 18, and participants positive for hrHPV other than 16 or 18.

Data obtained from participating GP clinics and laboratories.

*Timepoint:*

By six months after the end of the screening period.

---

### **Secondary outcome 20**

In participants that had a cytology test prior to colposcopy, the mean, median and range for the time from their cytology sample being undertaken to being informed of the result.

Data to be presented separately for participants negative for hrHPV, participants positive for HPV16 and/or 18, and participants positive for hrHPV other than 16 or 18.

Data obtained from participating GP clinics.

*Timepoint:*

By six months after the end of the screening period.

---

**Secondary outcome 21**

In participants that had a cytology test prior to colposcopy, the number (and percentage) informed of their cytology results by:

- Face to face appointment with a staff member at their GP clinic
- Phonenumber with a staff member from their GP clinic
- Text
- Other form of contact.

Data to be presented separately for participants negative for hrHPV, participants positive for HPV16 and/or 18, and participants positive for hrHPV other than 16 or 18.

Data obtained from participating GP clinics.

*Timepoint:*

By six months after the end of the screening period.

---

**Secondary outcome 22**

In participants that had a cytology test prior to their colposcopy referral, the mean, median and range for the time between the cytology result report being issued and referral for colposcopy.

Data to be presented separately for participants negative for hrHPV, participants positive for HPV16 and/or 18, and participants positive for hrHPV other than 16 or 18.

Data obtained from participating GP clinics and laboratories.

*Timepoint:*

By six months after the end of the screening period.

---

**Secondary outcome 23**

The number (and percentage) of participants that had a referral for colposcopy by classification of urgency.

Data to be presented separately for participants negative for hrHPV, participants positive for HPV16 and/or 18, and participants positive for hrHPV other than 16 or 18.

Data obtained from participating GP clinics.

*Timepoint:*

By six months after the end of the screening period.

---

#### **Secondary outcome 24**

In participants referred for colposcopy, the number (and percentage) that received 1, 2, 3 or >3 invitations for an appointment.

Data to be presented separately for participants negative for hrHPV, participants positive for HPV16 and/or 18, and participants positive for hrHPV other than 16 or 18.

Data obtained from colposcopy clinics.

*Timepoint:*

By six months after the end of the screening period.

---

